Study Protocol

Protocol Title: Utilization of Confocal Microscopy during Cardiac Surgery

Document Date: October 19, 2018

IRB Approval Date: October 31, 2018

NCT Number: NCT03189134

Utilization of Confocal Microscopy during Cardiac Surgery

A. Specific Aims/Objectives

This is a pilot study, exploring the safety and feasibility of using diluted fluorescein sodium with fiberoptic confocal microscopy during cardiac surgery.

- The primary aim of this study is to evaluate the safety of using diluted fluorescein sodium during cardiac surgery.
- A secondary aim of this study is to evaluate the feasibility of using this imaging modality. Feasibility will be evaluated in two ways: logistically and technologically.
 - Logistical feasibility will be evaluated by measuring increased time on bypass, rate of enrollment, and the ability to incorporate this imaging modality into standard OR procedures.
 - Technological feasibility will center on the ability to capture quality image files. A quality image file is defined as an image file where a rater can visualize the distinguishable features of the tissue type (cardiac tissue, conductive tissue) in order to classify that tissue type correctly.

B. Background and Significance

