Our research team is currently conducting experiments in sheep, but the data have not been published. In these studies, 3 sheep have been anesthetized and placed on cardiopulmonary bypass. Between 5-7mLs of 1:1000 diluted Fluorescite® was applied to the epicardium and endocardium, and images were obtained using the Cellvizio Imaging system. After the images were obtained, the animals were taken off bypass. ECGs were obtained at baseline, after re-perfusing the hearts, and after the animals were taken off bypass. The ECGs confirmed that after the procedure, the hearts resumed normal baseline cardiac activity. Visual examination of the hearts also confirmed normal ventricular function and vigorous activity. Furthermore, preliminary imaging data from these studies confirms that we are able to discriminate conduction tissue from the images taken.

D. Design and Methods

(1) Study Design

We propose a descriptive pilot study to assess the safety and feasibility of using fiber-optic confocal microscopy during cardiac surgery to image the endocardium and epicardium. 6 patients undergoing surgery for closure of atrial septal defect will be enrolled in this study.

All enrolled subjects will receive standard of care for cardiac surgery and the operation will be conducted according to routine procedure. After the sternotomy, the subject will be placed on cardiopulmonary bypass. After cardioplegic infusion and cardiac arrest, the right atrium will be opened to visualize the atrial septal defect.

At this juncture, fluorescein sodium at a concentration of 100ug/ml in sterile saline will be applied topically to the myocardium, where it will diffuse into the endocardium and epicardium. A total volume of 5ml will be applied. The surgeon will confirm there are no visual indicators of an allergic reaction to the fluorescein study drug. As long as there is no appearance of tissue damage, the imaging will proceed. If any signs of allergy or intolerance occur, the dye will be immediately flushed out and no images will be obtained.

The imaging probe of the Cellvizio system will then be applied in direct contact to the region of interest with minimal pressure for approximately 90 seconds. During this period, Cellvizio Software and Viewer will be used to obtain images. The total additional time on bypass will be approximately 3 minutes.

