Once the imaging procedure has been completed, the heart surface will be washed with saline and evacuated using a suction apparatus, to ensure all fluorescein has been removed and will

not enter the circulatory system. After that, the remainder of the operation will proceed in the usual fashion. As per standard of care for patients undergoing cardiac surgery, an intraoperative echocardiogram will be performed after the subject is separated from bypass.

The expected hospitalization for the Atrial Septal Defect (ASD) is 3-5 days post-operation. It is not expected that participation in this study will increase the post-operative hospital stay or post-hospitalization recovery. The principal investigator (PI) and research team will monitor clinical labs, electrocardiograms (EKGs), and echocardiograms for any evidence of adverse events. No additional follow-up testing, outside of standard clinical monitoring, are planned. In accordance with standard of care, all subjects will receive a pre-discharge EKG and trans-thoracic echocardiogram.

Image files will be exported out from the Cellvizio system, de-identified, and provided to the blinded raters. The image files will be assessed for quality and the ability to discriminate tissue types.

(2) Patient Selection and Inclusion/Exclusion Criteria

Patients undergoing cardiac surgery for ASD repair at Boston Children's Hospital will be enrolled in this study. Surgery for ASD repair exposes the conduction system of the heart, allowing access to the AWM and nodal tissue for image capture by the Cellvizio system. Congenital heart defects such as ASD are most often diagnosed and repaired in infants and children, which is why conducting this study in a pediatric population is appropriate. Additionally, the FCM has a pre-defined field of focus, with a depth ranging from 55 to 65 μm . Therefore, this technology is more suited to pediatric hearts, as adult hearts are thicker and the conductive tissue may be too deep to be identified using this method.

Inclusion criteria:

- Males and females between 30 days and 21 years old
- Undergoing elective surgery for closure of isolated secundum atrial septal defect
- Both parents attend pre-operative clinic appointment, to provide 2 parent consent, or an adult participant (age 18-21) may provide consent for him/herself

Exclusion criteria:

- Prior history of adverse reaction to fluorescein sodium
- Prior history of renal failure or abnormal renal function

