The probe will be used in direct contact with the cardiac tissue with a pressure of approximately 0.7 mmHg, which is less than 1% of diastolic blood pressure. The maximum laser energy that the system is capable of delivering is 15 mW at 480 nm. This power and wavelength has been approved by the FDA for direct in-vivo imaging for various body tissues, including gastrointestinal, urogenital, and pulmonary. The proposed application is approximately 80% less than the maximum allowable retinal exposure, according to the IEC 60825-1 standard.

(4) Definition of Primary and Secondary Outcomes/Endpoints

Primary Outcome: All adverse events will be collected and relatedness to study participation will be determined. Complications will be compared to average complication rates for ASD repairs.

Hypothesis: Subjects will not experience a higher rate of adverse events than is expected in a clinical setting (<3-4% for all types of adverse events).

Secondary Outcome: The logistical feasibility of conducting FCM imaging during cardiac surgery.

Hypothesis: The study procedure will be logistically feasible in terms of added time on bypass and the ability to incorporate FCM imaging into standard cardiac surgery OR procedures. The rate of enrollment will be evaluated separately.

Secondary Outcome: The quality of the FCM image files collected, defined as the ability of observers to distinguish features and discriminate between working myocardium and nodal tissue.

Hypothesis: Blinded raters will be able to use the FCM image files to distinguish features and discriminate between working myocardium and nodal tissue.

(5) Data Collection Methods, Assessments, Interventions and Schedule (what assessments performed, how often)

Standardized demographic and clinical assessments of all study participants will be performed via medical record review prior to and after surgery until the subject is discharged from the hospital. Images will be obtained during surgery and saved using Cellvizio Software and Viewer. The image files will be de-identified and provided to blinded raters for analysis. Medical records of enrolled subjects will be reviewed post-surgery while the subject is inpatient in the hospital. Adverse events will be abstracted from the record and recorded on a CRF and input into an InForm database.

(6) Study Timeline

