FCM image files obtained for the study will be stored on a password-protected hard drive connected to the Cellvizio system. The image files will be exported, labeled only with the subject's study ID number, and provided to the blinded raters for analysis.

G. Quality Control Method

All study related tasks will follow Good Clinical Practice guidelines. A manual of operations (MOO) will be developed to detail the specific procedures to be conducted and data to be collected. Any significant deviations or exceptions to the protocol will be reported to the IRB and FDA in addition to being discussed among the investigators, and the PI will develop and implement a plan of action as needed (e.g. modification to MOO, study amendment, etc.). The PI will ensure the retention of all necessary records and reports for a minimum of 2 years after the discontinuation of the IND. The FDA will be allowed access to these records. A record of accountability of all investigational drug dispositions will be maintained, including batch and lot numbers and storage records.

H. Data Monitoring

Monitoring and auditing procedures as outlined in the Monitoring Plan will be followed to ensure that the entire study is conducted, documented, and reported in accordance with the IRB approved protocol, the International Conference on Harmonization (ICH) Good Clinical Practice (GCP) Guidelines, and applicable regulatory requirements of Boston Children's Hospital.

Monitors will review and verify protocol compliance with particular focus on AE/SAE reporting, CRF data, source documentation, informed consents, and any other study-related documentation, including review of hospital pharmacy procedures, drug accountability documentation, and drug storage facilities and records.

I. Data Analysis Plan

The FCM image files will be provided post-surgery to blinded raters, who will attempt to categorize the image files as either myocardium or nodal tissue. The raters will note if the image quality is not high enough to discriminate tissue types.

J. Statistical Power and Sample Considerations

This is a single site, descriptive, pilot study, so no power calculations have been performed. Six subjects will provide enough images to determine the feasibility of a larger randomized trial, to be performed in the future.

K. Study Organization

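### Section A ties image quality to correct tissue classification, but the protocol requires no per-image site record and no reference comparison, so a right call cannot be told from a wrong one

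*Protocol*

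**What the plan says.** Section A (Specific Aims/Objectives) rests technological feasibility on quality image files, meaning files in which a rater can "visualize the distinguishable features of the tissue type (cardiac tissue, conductive tissue) in order to classify that tissue type correctly". D(4) lists image quality as a secondary outcome, worded as observers' ability to tell the two tissues apart, with the hypothesis: "Blinded raters will be able to use the FCM image files to distinguish features and discriminate between working myocardium and nodal tissue". For image classification, the word *correctly* stands only in section A.

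On acquisition, D(2) explains that this operation gives access to both atrial working myocardium and nodal tissue. D(1) has the probe "applied in direct contact to the region of interest with minimal pressure for approximately 90 seconds" and later states: "The image files will be assessed for quality and the ability to discriminate tissue types". D(5) says "Images will be obtained during surgery and saved using Cellvizio Software and Viewer" and mentions no site field. Under section F the exported files carry only the subject's "study ID number, and provided to the blinded raters for analysis".

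On analysis, section I gives the files to blinded raters, "who will attempt to categorize the image files as either myocardium or nodal tissue", and adds: "The raters will note if the image quality is not high enough to discriminate tissue types". No comparison with a known tissue type follows. Section G leaves procedural detail and data items to a manual of operations still to be written.

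**The concern.** A call is correct only relative to something known about the tissue under the probe. The protocol sets an endpoint that uses that idea and then requires data that cannot supply it. Section I yields two items per file: the rater's category and whether the rater found the quality sufficient. Neither shows whether the category is right.

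This is more than analysis detail that a later plan could add. An analysis plan can choose a statistic, but a probe site that nobody wrote down in the operating room may not be recoverable afterwards.

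Section J says that the images from six subjects are to inform the feasibility of a larger randomized trial, and the long-term purpose in section B is to identify conduction tissue during surgery. A high share of readable files could be carried forward as technological feasibility with no check that raters recognised the tissue.

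**Working it through.** **1. Trace of the endpoint.** The protocol states no accuracy target, so there is no figure to reproduce. The check is whether any step requires a site or tissue label.

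| Step | Section | Required | Site or tissue label per file? |
|---|---|---|---|
| Definition | A | Features visible so that tissue is classified correctly | Presupposed, not named |
| Targets | D(2) | Both tissues accessible | Named for the operation, not per file |
| Acquisition | D(1) | Probe on a region of interest | No |
| Data collected | D(5) | Images saved; record review; adverse events | No |
| Export | F | Study ID only | No |
| Analysis | I | Rater category; note on inadequate quality | No comparison |

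Reportable as written: the share of files judged readable, the share called each tissue, and between-rater agreement if several raters read the same file. Not reportable: the share of calls that match the tissue imaged.

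**2. What readability hides.** Suppose raters mark every file classifiable. Readability is then 100% for a rater who is right 50% of the time and equally for one at the level in section C (sensitivity 99.2%, specificity 98.0%). Between-rater agreement does not separate these cases reliably, because raters who share one wrong rule agree fully.

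**3. What a landmark key would show.** Let *a* be the share of rater calls that are right and *l* the share of landmark labels that are right. Assume independent errors and the same *a* for both tissues.

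Agreement = *a·l* + (1 − *a*)(1 − *l*)

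The values of *a* are 0.50 (coin toss) and the two figures from section C. The values of *l* are assumed; the protocol gives none.

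| *a* | *l* = 0.70 | 0.80 | 0.90 | 0.95 |
|---|---|---|---|---|
| 0.500 | 0.500 | 0.500 | 0.500 | 0.500 |
| 0.980 | 0.692 | 0.788 | 0.884 | 0.932 |
| 0.992 | 0.697 | 0.795 | 0.894 | 0.943 |

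For example, 0.980 × 0.70 + 0.020 × 0.30 = 0.686 + 0.006 = 0.692. An imperfect key still separates a good rater (69% to 94%) from a coin toss (50%).

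**4. Why pooled agreement is not enough.** An uninformative rater need not toss a coin. Assume that 80% of files are recorded as myocardium (the protocol gives no mix) and that a rater calls every file myocardium. Pooled agreement is 0.80 × 1 + 0.20 × 0 = 80%, inside the range of the good rater in step 3. Split by site, the same rater scores 100% on myocardium-site files and 0% on nodal-site files. Chance-corrected agreement is also zero: observed 0.80, expected 0.80 × 1 + 0.20 × 0 = 0.80, so kappa = (0.80 − 0.80)/(1 − 0.80) = 0.

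**5. Unclassifiable files.** The denominator matters. With assumed figures of 80% classifiable and 90% agreement among those, agreement over all acquired files is 0.80 × 0.90 = 72%, counting unclassifiable files as not in agreement.

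**The case against.** The strongest reply is that the case leans on one adverb. The clause in section A can be read as stating a purpose, and D(1) and D(4) speak only of discriminating tissue types. On that reading, a category and a quality flag are roughly what the outcome needs, and the defect is loose wording. This is a fair reading and it keeps the point modest. It does not remove it: discriminating two tissues also suggests calls that are right, and if readability alone is meant, section A promises more than is measured.

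A second reply is that a site key may well exist. Every subject is imaged in the same way, so tissue site is a plausible thing for raters to be blinded to, and stripping files down to a study ID is what such masking would need. The case report form or the manual of operations could hold the site. That stands, and it is why the point is limited to what the protocol requires.

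Three stronger readings are tempting and are not supported:

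- A reader might infer that a confidently misclassified file counts as a success. The protocol states no scoring rule or success threshold, and by section A's own definition such a file would not be a quality file. The required data simply cannot identify it.
- A reader might infer that the target tissues are unspecified. D(2) names both; only the link from each file to a tissue is missing.
- A reader might infer that a landmark key would measure accuracy. Section B describes discrimination by landmarks as limited and says that data on where these pathways lie in such hearts are sparse, so a key yields agreement with a fallible label.

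**Conclusion.** The point holds for the protocol as written. Section A defines image quality through correct classification, and no required data item or analysis step can distinguish a right call from a wrong one. The conclusion rests on the protocol text alone and lapses as a data gap if the manual of operations or case report form already captures the site; the protocol should then say so.

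On size, readability can stand at 100% while the share of right calls lies anywhere from 50% to the 98.0% to 99.2% reported in section C. The agreement figures in the working are illustrations that depend on the assumed landmark reliability, independent errors and an assumed tissue mix; they are not predictions for this trial.

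The weight is minor to moderate. It concerns one part of a secondary aim in a six-patient descriptive pilot. The primary safety aim, logistical feasibility and the capture of readable files are unaffected, so it would be wrong to infer that technological feasibility cannot be assessed at all.

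**What to change.** In D(1), D(5) and I, add a requirement such as: *the landmark-defined site of each image file (working myocardium or nodal region) is recorded at acquisition in a key withheld from the raters.* Then report:

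1. the share of all acquired files that raters judge classifiable;
2. agreement of rater calls with the recorded site, separately for nodal-site and myocardium-site files and by subject, both among classifiable files and among all acquired files with unclassifiable ones counted as not in agreement. A chance-corrected measure may be added.

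Call the second result agreement with landmark site, not accuracy, and do not set it directly against the sensitivity and specificity in section C. Besides the limits of landmarks, the first preliminary study in section C also used HCN4 labelling to identify nodal myocytes, and no counterpart is stated for patients.

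If no site will be recorded, delete *correctly* from section A and limit the conclusion to rater-judged readability.

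The cost is one extra field per file and short wording in three sections, or wording alone if the field already exists. Section K has one person acquiring all images, so one person can supply it. The drawback is that agreement mixes rater error with landmark error and may look lower than the preliminary figures.

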With several patients eligible weekly, it should be feasible to complete subject recruitment, enrollment, and follow-up within 6 months after study activation. Lead time will be needed to secure FDA and BCH Institutional Review Board (IRB) approval.

E. Adverse Event Criteria and Reporting Procedures

(1) Specification of Safety Parameters

Comprehensive assessments of any apparent toxicity experienced by the study subject will be performed throughout the course of the study. All safety events experienced by study subjects for the duration of the study will be documented. The types of adverse events that must be reported and procedures for appropriately recording, grading and reporting are outlined in this section.

(2) Definition of an Adverse Event (AE) or Medical Event

According to FDA regulations, an adverse event (AE) is any undesirable, noxious, or pathological change compared to preexisting conditions occurring to or in a study subject enrolled in a clinical trial, whether or not the event is considered related to the test drug. This includes the time periods during which no medication is administered to a study subject, such as run-in or follow-up periods. An adverse event is further defined as any change in structure (signs) or function (symptoms) of the body that occurs while the study subject is receiving study drug/placebo. AEs include the following types of changes:

- Suspected adverse drug reactions, which are any adverse events for which there is a reasonable possibility that the drug caused the adverse event. A reasonable possibility implies that there is evidence that the drug caused the event.
- Other medical experiences regardless of their relationship to the test drug, such as injury, surgery, accidents, extensions of symptoms or apparently unrelated illnesses, and significant abnormalities in clinical laboratory values, physiological testing, or physical examination findings.

(3) Definition of Serious Events (Serious Adverse Events, Serious Suspected Adverse Reactions or Serious Adverse Reactions)

A serious adverse event including a serious suspected adverse reaction or serious adverse reaction as determined by the Investigator or the sponsor is any event that results in any of the following outcomes:

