We will assign toxicity grades to indicate the severity of adverse experiences and toxicities. Toxicity grading consistent with NCI-CTCAE v 4.03 will be used for this protocol. The purpose of using the NCI-CTCAE system is to provide standard language to describe toxicities and to facilitate tabulation and analysis of the data and assessment of the clinical significance of treatment-related toxicities.

Adverse events not included in the NCI-CTCAE listing will be recorded and graded 1 to 5 according to the General Grade Definition provided below:

Grade 1	Mild	Transient or mild discomforts (< 48 hours), no or minimal medical intervention/therapy required, hospitalization not necessary (non-prescription or single-use prescription therapy may be employed to relieve symptoms, e.g., aspirin for simple headache, acetaminophen for post-surgical pain).
Grade 2	Moderate	Mild to moderate limitation in activity, some assistance may be needed; no or minimal intervention/therapy required, hospitalization possible.
Grade 3	Severe	Marked limitation in activity, some assistance usually required; medical intervention/therapy required, hospitalization possible.
Grade 4	Life-threatening	Extreme limitation in activity, significant assistance required; significant medical/therapy intervention required, hospitalization, or hospice care probable.
Grade 5	Death	Death

For additional information and a printable version of the NCI-CTCAE v. 4.03 manual, consult the NCI-CTCAE website, <http://ctep.cancer.gov/reporting/ctc.html>.

(6) Guidelines for Determining Causality of an Adverse Event

The Investigator will use the following question when assessing causality of an adverse event to study drug: Is there a reasonable possibility that the drug caused the event? An affirmative answer designates the event as a suspected adverse reaction.

If there is any doubt as to whether a clinical observation is an AE, the event should be reported. All AEs must have their relationship to study product assessed using the terms related or not related. In a clinical trial, the study product must always be suspect. To help assess, the following guidelines are used:

- Related – Related means there is evidence to show a causal relationship between the study product and the adverse event.

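### D(4) compares complications in the outcome but adverse events in the hypothesis, and on either count six subjects cannot support a rate no higher than 3-4%

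*Protocol*

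**What the plan says.** The primary outcome in D(4) starts with collection: "All adverse events will be collected and relatedness to study participation will be determined". It then names the comparison: "Complications will be compared to average complication rates for ASD repairs". The hypothesis beneath it changes the category: "Subjects will not experience a higher rate of adverse events than is expected in a clinical setting (<3-4% for all types of adverse events". No reference accompanies the 3-4%, and no unit is given.

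The surrounding sections set how wide each category is:

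- **E(2)** says that an adverse event "is any undesirable, noxious, or pathological change compared to preexisting conditions occurring to or in a study subject enrolled in a clinical trial", and adds "whether or not the event is considered related to the test drug". Significant laboratory and examination findings are included.
- **E(4)** lists common complications of ASD repair, such as tamponade, bleeding and stroke. The list is introduced by examples and carries no rates. The same paragraph then refers to these complications as adverse events and classes them as expected and unrelated to the study drug.
- **E(5)**, in its Grade 1 definition for events outside CTCAE, illustrates minimal therapy with "aspirin for simple headache, acetaminophen for post-surgical pain".

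On size, D(1) states: "6 patients undergoing surgery for closure of atrial septal defect will be enrolled in this study". Section J states: "This is a single site, descriptive, pilot study, so no power calculations have been performed". It justifies the six by the images needed to judge feasibility.

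**The concern.** Safety is the primary aim, and this is its only stated hypothesis. It has two weaknesses.

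First, the numerator and the benchmark may not describe the same thing. The outcome sentence suggests that 3-4% is a complication rate. The hypothesis applies it to adverse events of every type, which under E(2) take in much more. A broad count set against a narrow benchmark can show an excess that has nothing to do with the dye or the probe.

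Second, the hypothesis claims the absence of an increase. With six subjects, the best possible result is also compatible with rates many times the benchmark. A reader who took zero events as confirmation would carry an unsupported safety statement into the larger randomized trial that section J anticipates.

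**Working it through.** **No figure to reproduce.** The protocol gives no derivation for six subjects or for 3-4%, and no alpha, margin or confidence level. The 95% level is assumed here. The unit assumed is the proportion of subjects with at least one event.

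**Inputs.** n = 6 (D(1)); benchmark 3% to 4% (D(4)).

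**Step 1: the categories side by side.**

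| Place | Category |
|---|---|
| D(4), what is collected | all adverse events |
| D(4), what is compared | complications |
| D(4), hypothesis | adverse events, all types |
| E(2) | any undesirable change, related or not |
| E(4) | listed complications, also called adverse events |

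The outcome and the hypothesis agree only if adverse events in the hypothesis is read in the narrow E(4) sense, which D(4) does not say.

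**Step 2: exact (Clopper-Pearson) limits for x of 6.** The lower limit is the 0.025 quantile of Beta(x, 7 - x), and the upper limit is the 0.975 quantile of Beta(x + 1, 6 - x).

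| Subjects with an event | Observed | Two-sided 95% CI | Against 3-4% |
|---|---|---|---|
| 0/6 | 0% | 0% to 45.9% | includes it |
| 1/6 | 16.7% | 0.4% to 64.1% | includes it |
| 2/6 | 33.3% | 4.3% to 77.7% | lies above 4% |

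For 0/6 the upper limit has a closed form: 1 - 0.025^(1/6) = 0.459 two-sided, and 1 - 0.05^(1/6) = 0.393 one-sided. Since 39.3/4 = 9.8, even the one-sided limit is about ten times the upper end of the benchmark.

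**Step 3: how often each result occurs.** P(0) = (1 - p)^6 and P(2 or more) = 1 - (1 - p)^6 - 6p(1 - p)^5.

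| True per-subject rate p | P(0/6) | P(at least 1) | P(at least 2) |
|---|---|---|---|
| 3% | 83.3% | 16.7% | 1.2% |
| 4% | 78.3% | 21.7% | 2.2% |
| 10% (assumed) | 53.1% | 46.9% | 11.4% |
| 20% (assumed) | 26.2% | 73.8% | 34.5% |
| 40% (assumed) | 4.7% | 95.3% | 76.7% |
| 50% (assumed) | 1.6% | 98.4% | 89.1% |

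The protocol gives no any-grade adverse event rate, so rows from 10% down are illustrations. They show two things. If minor events are common, two or more subjects with an event is a likely result whatever the study procedure does. And 0/6, the best result, is still more likely than not at a true 10%.

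**Step 4: scale.** With no events at all, the one-sided 95% upper limit falls below p once n reaches ln(0.05)/ln(1 - p), rounded up: 74 subjects for 4% and 99 for 3%. This shows how far the claim is from what a pilot can deliver; it is not a proposed sample size.

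**Step 5: other units.** If 3-4% is meant for each event type separately, Step 2 applies to each type in turn, and zero subjects with a given type still leaves 39.3% or 45.9%. If it is meant per event, the binomial no longer applies. Under a Poisson assumption, zero events in six subjects leaves a one-sided upper limit of -ln(0.05)/6 = 0.50 events per subject. No reading makes the hypothesis supportable.

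**The case against.** The strongest reply is that this is loose terminology in a pilot that never claims to test anything. E(4) itself calls the listed complications adverse events, so the hypothesis may mean complications throughout. D(4) also separates what is collected from what is compared, which argues against a count of every minor event. The analgesic example in E(5) is a parenthesis in a severity scale; it does not say that routine pain enters the primary comparison. The benchmark may be meant per event type, which would explain its odd form. The hypotheses in D(4) read as informal expectations, and details of interval estimation can properly sit in an analysis plan that is not shown.

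Much of this stands. It lowers confidence about which mismatch was intended, and it rules out treating the any-event count as the only reading. It does not rescue the hypothesis. Read narrowly, the categories agree, but 0/6 still cannot support the claim. Read broadly, the categories disagree. An analysis plan could follow the outcome sentence or the hypothesis, but would have to depart from one of them on the broad reading.

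A reader might also infer that six subjects is too few, or that omitting a power calculation is an error. The documents do not support that: section J declares a descriptive pilot and justifies the number by feasibility. Nor do they support the inference that a spurious excess would halt enrolment. The DSMB review triggers in E(6) and the reporting duties in E(7) do not refer to 3-4%.

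**Conclusion.** The point holds as an inconsistency in D(4) that should be fixed. The outcome and the hypothesis name different categories, the benchmark has neither source nor unit, and the comparative claim cannot be supported by any result in six subjects. On an any-event count, two subjects with minor events (4.3% to 77.7%) would look like an excess that may be only an artefact of the mismatch. On a complication count, 0/6 excludes only rates above 39.3% (one-sided) or 45.9% (two-sided).

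This rests on a per-subject unit and a 95% level, both assumed. That 3-4% is a complication rate is an inference from the preceding sentence. It would go too far to say that the any-event rate will certainly exceed 3-4%, because the protocol gives no such rate, or that the investigators will report 0/6 as proof of safety, because no passage says so. The effect is confined to what the pilot may conclude on its primary aim.

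**What to change.** Reword D(4) so that the outcome and the hypothesis use one category: subjects with at least one post-operative complication. Define it by the E(4) list, made explicit instead of given as examples; without that definition the category stays open. Count these events whatever relatedness is assigned, because E(4) declares them unrelated in advance.

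Replace the comparative hypothesis with a descriptive statement along these lines: the number of subjects out of six with at least one listed complication will be reported with an exact 95% CI; the ASD-repair complication rate, with its source, unit and matching definition, is shown as context only; all other adverse events, including those named in E(6), are reported descriptively without a benchmark; zero of six would exclude only rates above about 39% (one-sided) or 46% (two-sided).

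The change needs no further patients and no new data. Its cost is a weaker stated safety claim, which is as much as six subjects can support.
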